Appendix

GM-CSF Pharmacology

GM-CSF Preclinical Toxicology

GM-CSF Pharmacokinetics in Normal Subjects

Protocol Title	Neoadjuvant GM-CSF treatment and modulation of the immune		
	cell profile of the SLN in melanoma (as above)		
# Site and Names:	One Site: Mayo Clinic Rochester		
Study Schema:	Twenty patients with a primary melanoma 1-4mm Breslow depth		
	will be randomized to either undergo standard care (10 patients),		
	or be treated with 14 days of GM-CSF administered		
	subcutaneously daily in a dose of 125 μ g/m ² preoperatively (10		
	patients), prior to sentinel lymph node biopsy. The regional lymph		
	nodes will undergo detailed analysis defining their immune		
	features		
Trial Objective:	features To characterize and compare the regional nodal immune features		
Trial Objective:	features To characterize and compare the regional nodal immune features of the GM-CSF treated patients, including the Th1/Th2		
Trial Objective:	features To characterize and compare the regional nodal immune features of the GM-CSF treated patients, including the Th1/Th2 environment, with the regional immune environment of the		
Trial Objective:	features To characterize and compare the regional nodal immune features of the GM-CSF treated patients, including the Th1/Th2 environment, with the regional immune environment of the control cohort		
Trial Objective:	features To characterize and compare the regional nodal immune features of the GM-CSF treated patients, including the Th1/Th2 environment, with the regional immune environment of the control cohort		
Trial Objective: Study Design:	features To characterize and compare the regional nodal immune features of the GM-CSF treated patients, including the Th1/Th2 environment, with the regional immune environment of the control cohort Open-label, single-center, randomized controlled trial		
Trial Objective: Study Design: Accrual Goal:	features To characterize and compare the regional nodal immune features of the GM-CSF treated patients, including the Th1/Th2 environment, with the regional immune environment of the control cohort Open-label, single-center, randomized controlled trial 20 patients		

PROTOCOL SYNOPSIS

Followup:	30 days postoperatively			
Inclusion Criteria:	Histologically confirmed, 1-4mm Breslow depth			
	melanoma			
	Clinical stage I or II disease			
	Undergoing sentinel lymph node biopsy			
Exclusion Criteria	Clinical stage III or IV disease			
	Immunosuppressive therapy in the past 6 weeks (e.g.			

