We have previously demonstrated that SLNs in melanoma are fundamentally immunologically distinct from normal lymph nodes; the SLNs consistently have less expression of Th1 transcription factor T-bet and almost complete absence of cytotoxic T cells and mature antigen presenting cells (CD86⁺) (Grotz et al., 2012; Mansfield et al., 2011). Th2 cytokines depress macrophage and T cell activation and function, and as such are independent predictors of poor prognosis in melanoma (Cochran et al., 2006). We have shown this regional nodal immune dysfunction occurs in cases with and without evidence of lymph node metastases (Mansfield et al., 2011). In particular, immunohistochemical analysis indicated that cytotoxic T cell accumulation within the SLN declines early in melanoma and that the degree of CD8 depletion corresponds to the risk of disease recurrence (unpublished data). Furthermore, there is a Th2 skewed cytokine expression within the SLNs of patients with melanoma compared to control lymph nodes. These changes precede SLN metastasis and we theorize are necessary for regional spread of disease. Other studies have confirmed that exposure of peripheral

blood monocytes to melanoma produces a Th2-type cytokine profile. Cytokine analysis of SLN from melanoma demonstrates an initial increase in GM-CSF observed in SLNs could lead to the attraction of a high number of dendritic cells (DC to SLNs). However, the presence of immunosuppressive molecules, such as IL-10 and COX-2, could block their maturation and prohibit their ability to become efficient antigen presenters.

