The intervention group will be issued a 14 day supply of GM-CSF to self-administer daily. They will be provided phone numbers and details of who to contact with any concerns for adverse events, as well as a diary in which to record time of administration, whether entire vial was injected, and any adverse events. Patients will be provided a list of adverse events and to call immediately for any grade 3 or high adverse event. Grade I-II AEs will be logged into their diary. The diary will be collected on the day of surgery.

Patients in the control arm, who have been randomized to not undergo preoperative GM-CSF, will not receive GM-CSF in the preoperative phase.

Surgery

Patients will undergo formal consent for their operative procedure which will be separate from the consent for trial enrollment. Patients will undergo sentinel lymph node biopsy and the sentinel lymph nodes will be sent to pathology. The lymph node (LN) will undergo gross sectioning along the long axis at 1-2mm intervals until the LN is exhausted. The sections are then placed on a cryotome where they freeze from the bottom up. Prior to freezing, the top of one of these 2mm sections will be divided in half. One half will be reviewed by pathologists, the other half will be submitted for research. The remaining sections of the lymph node will be examined by standard pathological analysis. Sentinel lymph node number one will be the preferred SLN from which tissue will be collected, unless it is < 7mm in greatest dimension, in which cases sequential SLNs will be evaluated for gross size and $\frac{1}{2}$ of a top will be taken from the next SLN with a gross size \geq 7mm as described above. If all SLNs are <7mm tissue will not be collected for research. In addition, if there is any fresh or frozen tissue in excess of diagnosis and not critical to the pathologic interpretation this should be submitted for research purposes as well. If there is no remaining fresh or frozen tissue then paraffin fixed tissue will be collected after pathological diagnosis for this study. Only tissue from SLN #1 and if applicable SLN #2 will be submitted for research purposes. The tissue specimen will be submitted fresh for research purposes as described below and as is our practice with TRAG approval for our currently active study (IRB 10-000806).

Laboratory analysis

Lymph node tissue analysis

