Primary endpoint: The primary endpoint is the Th1/Th2 ratio. Th1/Th2 ratio will be compared between the two groups. The trial will be considered a success if the Th1/Th2 ratio is statistically significantly higher in the GM-CSF treated group.

Sample Size and power: There will be 10 patients in each group. It is expected that this treatment will have a considerable effect on the Th1/Th2 ratio. If it does not, it will not be of further interest. A sample size of 10 in each group will have 80% power to detect an effect size of 1.325 using a two group t-test with a 0.050 two-sided significance level. The effect size is the expected difference in the means divided by the pooled standard deviation.

Analysis plan: The primary endpoint will be compared between the two groups using a two-sample t-test. If the distribution of the Th1/Th2 ratios is considerably skewed, the analysis will be done on the log transformed values. If the log transformed distribution is also skewed, then a rank-sum test will be used to compare the Th1/Th2 values between the two groups. Given the small sample size, all other analyses will be exploratory. Continuous measurements will be summarized with means and standard deviations and compared between groups using a two-sample t-test (on log transformed data if necessary). Categorical variables will be summarized as frequencies and relative frequencies and will be compared between groups with a Fisher's exact test. We will also summarize disease-free survival with Kaplan-Meier curves. The adverse event data will be reported as frequencies and relative frequencies. The number/proportion of patients with Grade 3+ AEs will be compared between the two groups using Fisher's exact test. All tests will be two-sided and a p-value of 0.05 will be considered statistically significant.

PROJECTED RESULTS

We will compare demographic, clinical and pathological variables between the two cohorts. Given the unselected nature of this study we anticipate that the two groups will be comparable.

We anticipate that the gene expression phenotype (as analyzed by RT-PCR) and the immune milieu (as analyzed by flow cytometry) of the SLN in patients who received preoperative GM-CSF will have maintained a more Th1 biased immune profile. We

anticipate that the improved Th1:Th2 profile will not only apply to the SLN but to neighboring lymph nodes as well.

Data Management Plan

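### Does leaving the skewness trigger and the scale of the 1.325 effect unstated endanger the primary Th1/Th2 comparison?

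*Combined protocol and SAP*

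**What the plan says.** All of the relevant text is in Statistical Considerations, apart from one line in the synopsis.

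- **Primary endpoint:** "The trial will be considered a success if the Th1/Th2 ratio is statistically significantly higher in the GM-CSF treated group".
- **Analysis plan:** a two-sample t-test comes first. Then "If the distribution of the Th1/Th2 ratios is considerably skewed, the analysis will be done on the log transformed values", and "If the log transformed distribution is also skewed, then a rank-sum test will be used to compare the Th1/Th2 values between the two groups". All tests are two-sided at 0.05, and every other analysis is exploratory.
- **Sample Size and power:** 10 patients per arm give 80% power at an effect size of 1.325, defined as follows: "The effect size is the expected difference in the means divided by the pooled standard deviation". The section expects a considerable effect on the ratio and adds "If it does not, it will not be of further interest".
- **Protocol Synopsis:** the design is "Open-label, single-center, randomized controlled trial". The Statistics entry repeats 1.325 but attaches it to mRNA expression and cell-type prevalence, not to the ratio.

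**The concern.** Success rests on one p-value from 20 patients, and which test supplies it depends on a judgement about skewness. The plan names no statistic or cut-off. It does not say whether skewness is judged within arms or on all values together, and it names no assessor masked to arm. Someone who knew the allocation could, in principle, see three p-values and then decide how skewed the data were.

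There are two lesser worries. The plan has no rule for a Th1 or Th2 transcript that is not detected, although the Background reports that "the SLNs consistently have less expression of Th1 transcription factor T-bet". And 1.325 is given without an SD, a fold change or a named scale, so a reader cannot translate it into laboratory terms, although the power section says that a treatment without a considerable effect would be dropped.

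If these gaps were serious, the false-positive rate could be well above 5%, the real power could be well below 80%, or a null result could be read as ruling out effects that the trial cannot see.

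**Working it through.** **Inputs from the plan:** 10 per arm, two-sided 0.05, effect size 1.325, and the order raw t, log t, rank-sum. The plan gives no SD or distribution, so the distributions and cut-offs below are assumptions.

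**1. The plan's own figure.** Degrees of freedom = 10 + 10 − 2 = 18, and the critical t is 2.101. Noncentrality = 1.325 × √(10/2) = 2.963. Exact noncentral-t power is 0.800, so the stated 80% is reproduced.

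**2. The rule as written, with a cut-off filled in.** Use the raw t if absolute skewness is at most c, otherwise the log t if the logs' absolute skewness is at most c, otherwise the rank-sum. Skewness is taken on all 20 values (pooled) or on values less their arm mean (centred). The table comes from 40,000 simulated trials per setting. Each cell is type I error / power at 1.325, in per cent; the effect is on the log scale for log-normal ratios and on the raw scale for normal ones.

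| Cut-off, basis | Log-normal, log-SD 0.5 | Log-normal, log-SD 1.0 | Normal |
|---|---|---|---|
| 0.5, pooled | 5.1 / 78.8 | 4.8 / 78.5 | 4.9 / 79.1 |
| 0.5, centred | 5.8 / 80.5 | 5.4 / 79.9 | 5.3 / 80.2 |
| 1, pooled | 5.1 / 79.0 | 5.0 / 79.2 | 5.1 / 80.1 |
| 1, centred | 5.5 / 80.3 | 5.5 / 80.3 | 5.3 / 80.4 |
| 2, pooled | 4.9 / 77.1 | 4.8 / 75.6 | 5.0 / 80.2 |
| 2, centred | 4.9 / 76.9 | 4.7 / 74.7 | 5.1 / 80.2 |

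Simulation error is about 0.1 point for type I error and 0.2 point for power. Extending log-normal ratios to log-SD 1.3 takes the lowest power at a cut-off of 2 to about 73%; cut-offs of 0.5 and 1 still give about 78 to 81%.

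**3. Worst case for an unmasked choice.** Declaring significance if any of the three tests reaches it gives 5.9 to 6.5% two-sided error. The three tests use the same data and usually agree, which is why the rise is small. Success counts only when the ratio is higher with GM-CSF; in that direction the rate is 3.1 to 3.3% (log-SD 0.5 to 1.3), against 5% / 2 = 2.5%.

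**4. How often the cut-off decides the verdict.** At the true effect, moving between 0.5 and 1 and between the two bases changes the verdict in 4 to 5% of trials for log-normal ratios and 2% for normal ratios.

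**5. What 1.325 means.** On the log scale the ratio of geometric means is exp(1.325 × log-SD): exp(0.6625) = 1.9 at log-SD 0.5, exp(0.9275) = 2.5 at 0.7, and exp(1.325) = 3.8 at 1.0. A true doubling is an effect of ln 2 / log-SD, that is 0.693/0.5 = 1.386, 0.693/0.7 = 0.990 and 0.693/1.0 = 0.693. The power for a doubling is then 83%, 55% and 31%.

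**The case for a change.** The best case for a change has three parts.

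**The cut-off is not neutral if read loosely.** With strongly skewed ratios (log-SD 1.0) the raw t-test alone has 56.9% power against 79.9% for the log t, and if a cut-off of 2 is allowed, verdicts differ in 7 to 11% of log-normal trials. The figures are right, but the low power needs an analyst who keeps the raw test in plainly skewed data. At log-SD 1.0 and the target effect, skewness exceeds 1 in 79 to 93% of trials, depending on the basis. Some dependence of borderline verdicts on the rule remains, as it does with any data-driven choice of test.

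**Undetected values.** A zero has no logarithm, a zero denominator gives no ratio, and the plan is silent on both. With log-SD 0.7 and 5% of values 3 log units lower, power falls to 63 to 68% and verdict changes reach 10%. Nothing in the documents supports that setting. The Background reports lower T-bet expression than in normal nodes, not absent expression. The assay in Laboratory analysis uses stimulated, CD4-selected cells and arrays of Th1 and Th2 mRNAs. The silence is real, but its likelihood cannot be judged from the documents, and sending the analysis to the rank-sum step would not by itself define a ratio whose denominator is missing.

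**The target cannot be read in fold-change terms.** This is the strongest part: a null result might leave a doubling open. But the sentence about further interest concerns a treatment that lacks a considerable effect. It does not equate a non-significant p-value with abandonment, and the only decision rule is the one for success. The documents give no SD from which a fold change could be derived, and Laboratory analysis does not fix which transcripts form the ratio. The synopsis wording is a mismatch of variables only: sample size, test, level and effect size are the same in both places, so the arithmetic is the same.

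**Conclusion.** The observation is accurate, but it calls for no change. The plan fixes a sound order of tests in advance and leaves the skewness threshold to the analyst. With a cut-off of 0.5 or 1, on either basis, error stays between 4.8 and 5.8% and power within about two points of the planned 80%. A lax reading costs 3 to 7 points of power under log-normal ratios (80 − 77 to 80 − 73). Deliberate selection among the tests would add at most about 1.5 points of two-sided error (6.5 − 5.0). For a 20-patient mechanistic trial with a single primary comparison, that is small.

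Writing down a cut-off would not be a better method. Centring on arm means raises error slightly, and the pooled basis gives up about a point of power under log-normal ratios. Fixing the log t in advance would itself lose power if the ratios were normal on the raw scale (75 to 78%).

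The standardised target is defined, its power is correct, and the first-listed untransformed t-test points to the raw scale. A fold change would need an SD that the documents do not contain.

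These sizes rest on assumed log-normal or normal ratios with no undetected values; the documents give no data with which to check that.

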Appendix

GM-CSF Pharmacology

GM-CSF is a human granulocyte-macrophage colony stimulating factor (rhu GM-CSF) produced by recombinant DNA technology in a yeast (S. cerevisiae) expression system. It is a glycoprotein of 127 amino acids characterized by three primary molecular species having molecular masses of 19,500, 16,800 and 15,500 daltons. The amino acid sequence of GM-CSF differs from the natural human GM-CSF by a substitution of leucine at position 23, and the carbohydrate molety may be different from the native protein. GM-CSF belongs to a group of growth factors termed colony stimulating factors which support survival, clonal expansion, and differentiation of hematopoietic progenitor cells (Metcalf et al., 1986). GM-CSF induces partially committed progenitor cells to divide and differentiate in the granulocyte-macrophage pathways which include neutrophils, monocytes/macrophages and myeloid-derived dendritic cells. GM-CSF is also capable of activating mature granulocytes and macrophages. GM-CSF is a multilineage factor and, in addition to dose dependent effects on the myelomonocytic lineage, can promote the proliferation of megakaryocytic and erythroid progenitors. However, other factors are required to induce complete maturation in these two lineages. The various cellular responses (i.e., division, maturation, activation) are induced through GM-CSF binding to specific receptors expressed on the cell surface of target cells (Park et al., 1986).

GM-CSF Pre-Clinical Toxicology

The biological activity of GM-CSF is species-specific. Consequently, in vitro studies have been performed on human cells to characterize the pharmacological activity of GM-CSF. In vitro exposure of human bone marrow cells to GM-CSF results in the proliferation of hematopoletic progenitors and in the formation of pure granulocyte, pure macrophage and mixed granulocyte-macrophage colonies. Chemotactic, anti-fungal and antiparasitic activities of granulocytes and monocytes are increased by exposure to GM-CSF in vitro (Reed et al., 1987). GM-CSF increases the cytotoxicity of monocytes toward certain neoplastic cell lines (Grabstein et al., 1986) and activates polymorphonuclear neutrophils to inhibit the growth of tumor cells. Pharmacology/toxicology studies of GM-CSF were performed in cynomolgus monkeys. An acute toxicity study revealed an absence of treatment-related toxicity following a single IV bolus injection at a dose of 300 mcg/kg. Two subacute studies were performed using IV injection (maximum dose 200 mcg/kg/day × 14 days) and subcutaneous injection (SC) (maximum dose 200 mcg/kg/day × 28 days). No major visceral organ toxicity was documented. Notable histopathology findings included increased cellularity in hematologic organs and heart and lung tissues. A dose-dependent increase in leukocyte count, which consisted primarily of segmented neutrophils, occurred during the dosing period; increases in monocytes, basophils, eosinophils and lymphocytes were also noted. Leukocyte counts decreased to pretreatment values over a 12 week recovery period.

GM-CSF - Pharmacokinetics in Normal Subjects

Pharmacokinetic profiles have been analyzed in controlled studies of 24 normal male volunteers (Spitler et al., 2012). Liquid and lyophilized GM-CSF, at a dose of 250 mcg/m2, has been determined to be bioequivalent based on the statistical evaluation of AUC. When GMCSF (either liquid or lyophilized) was administered IV over two hours to normal volunteers, the mean beta half-life was approximately 60 minutes. Peak concentrations of GM-CSF were observed in blood samples obtained during or

immediately after completion of GM-CSF infusion. For liquid GM-CSF, the mean maximum concentration (Cmax) was 5.0 ng/mL, the mean clearance rate was approximately 420 mL/min/m2 and the mean AUC (0inf) was 640 ng/mL•min. Corresponding results for lyophilized GMCSF in the same subjects were mean Cmax of 5.4 ng/mL, mean clearance rate of 431 mL/min/m 2, and mean AUC (0inf) of 677 ng/mL•min. GM-CSF was last detected in blood samples obtained at three or six hours. When GM-CSF (either liquid or lyophilized) was administered SC to normal volunteers, GM-CSF was detected in the serum at 15 minutes, the first sample point. The mean beta half-life was approximately 162 minutes. Peak levels occurred at one to three hours post injection, and GM-CSF remained detectable for up to six hours after injection. The mean Cmax was 1.5 ng/mL. For liquid GM-CSF, the mean clearance was 549 mL/min/m2 and the mean AUC (0inf) was 549 ng/mL•min. For lyophilized GM-CSF, the mean clearance was 529 mL/min/m 2 and the mean AUC (0inf) was 501 ng/mL•min. The pharmacokinetic profile of the EDTA-containing GM-CSF formulation is not the same as that of reconstituted lyophilized and previous liquid formulations. These differences include an earlier Tmax, a decrease in clearance and two peaks of absorption as compared to a single peak of the other formulations. The magnitude of these differences is small and unlikely to result in meaningful pharmacodynamic changes. This difference is attributed to the presence of EDTA in GM-CSF.
